## Experimental Design Schema

	Pre-Study (up to 28 days prior to enrolling) i	Cycle 1 Day 1 (28 day cycle)	Cycle 1 Day 8 (± 1 day)	Cycle 1 Day 15 (± 1 day)	Cycle 2 Day 1 (± 3 days)	Cycle 2 Day 15 (± 3 days)	Cycle 3 Day 1 (± 3 days)	Cycle 4 Day 1 (± 3 days)	Cycle 5 Day 1 (±3 days)	Cycle 6 Day 1 (±3 days)	Every Cycle Thereafter (± 3 days)	Every 3 cycles (±7 days)	Off treatment h
Neratinib (day 1-28 every 4 weeks a,b )		X	X	X	X	X	X	X	X	X	X		
Demographics	X												
Medical history	X												
Concurrent meds (± 1 wk)	X	X			X		X	X	X	X	X		X
Physical exam (± 1 wk)	X	X			X		X	X	X	X	X		X
Vital signs (± 1 wk)	X	X			X		X	X	X	X	X		X
Height	X												
Weight (± 1 wk)	X	X	X	X	X	X	X	X	X	X	X		X
Performance Status (± 1 wk)	X	X			X		X	X	X	X	X		X
CBC w/diff, plts (± 1 wk)	X	X			X		X	X	X	X	X		X
Complete Metabolic Panel c (± 1 wk)	X	X	X	X	X	X	X	X	X	X	X		X
Diarrhea Checklist		X l											
Nurse brief toxicity evaluation		X	X	X	X	X	X						
EKG	X												
Pharmacokinetic samples j				X			X	X					
Adherence evaluation (pill count, diaries) (± 1 wk)		X	X	X	X	X	X	X	X	X	X		
Adverse event evaluation (± 1wk)		X	X	X	X	X	X	X	X	X	X		X
Tumor measurements using CT or PET-CT (± 1 wk)	X d							X				X e	X f
LVEF Assessment	X d							X e				X e	X f

Geriatric Assessment Survey( $\pm 1$ wk) k	X						X					X g
Peripheral Blood Correlatives k	X						X					X
Bacteriomic profiling	X m			X	X	X	X					

a: Dose as assigned; neratinib 240mg orally daily; Doses held due to toxicity will not be made up.

b: If baseline laboratory tests are done within 14 days of start of treatment, these labs do not need to be repeated prior to Day 1.

c: Albumin, alkaline phosphatase, total bilirubin, bicarbonate, BUN, calcium, chloride, creatinine, glucose, potassium, total protein, SGOT[AST], SGPT[ALT], sodium.

d: Baseline assessment may be done up to 30 days prior to study enrollment.

e: Tumor measurements and LVEF assessment are repeated every 3 cycles  $\pm 1$  wk until patient comes off study. Documentation (radiologic or clinical) must be provided for patients removed from study for progressive disease.

f: Off-study radiologic evaluation will only be done if clinically indicated.

g: Geriatric assessment will be performed at baseline prior to study, after 3 cycles and at end of study. Geriatric assessment will be repeated off study ONLY if it had not been administered within the previous month. If patient's native language was not covered by the current language forms, Geriatric assessment form can be omitted with clear documentation.

h: Patients will be followed for 30 days following discontinuation of therapy in order to capture toxicity attributable to therapy.

i. Chart review data must be within 28 days to determine if patient meets study criteria. Once patient meets study criteria, then all criteria must be within window specified in protocol from Day 1 as indicated in column one in the schema above.

[figure not shown]
j: Pharmacokinetics samples will be collected at the following time points: Cycle 1 Day 15 pre-dose ( $\pm 20$  minutes) and 6 hours post-dose ( $\pm 60$  minutes); pre-dose ( $\pm 20$  minutes) on Cycle 3 Day 1 and Cycle 4 Day 1. All pre-dose samples should be collected within 30 minutes before the daily dose, in 10 ml purple-top tube.

k: Peripheral blood correlatives for inflammatory marker measurement (IL-6, CRP and D-dimer) and ctDNA will be collected at baseline, after 3 cycles (Cycle 4 Day 1, $\pm 7$  days), and at end of study ( $\pm 7$  days) when patient receives geriatric assessment in 10 ml purple-top tube.

L: An "Optimal Management of Diarrhea Checklist" will be reviewed and signed by study investigator or study nurse on Cycle 1 Day 1. The study team will call patients at 1 day, 2 days and 3 days after first dose of neratinib to assess tolerance.

m. Stool samples must be collected within 7 days prior to start of neratinib, at onset of first episode of diarrhea (same day), C1Day 15 (+/-3 days), C2Day1 (+/-3 days), C2Day15 (+/-3 days), C3Day1 (+/-3 days).

## Study Schema

## Protocol Synopsis

Protocol Title:
PHASE II STUDY OF NERATINIB IN PATIENTS 60 AND OLDER WITH HER2 POSITIVE METASTATIC BREAST CANCER
Brief Protocol Title for the Lay Public (if applicable):
Neratinib in Older Adults
Study Phase:
Phase II
Participating Sites:
City of Hope Comprehensive Cancer Center
Rationale for this Study:

Limited evidence exists to guide therapy with targeted agents in the older adult because these patients have been under-represented in clinical trials. Adults age 70 and older make up only 20% of subjects enrolled in FDA registration trials, but 46% of all patients with cancer are older adults. Dose-finding studies specifically in older adults are not routinely performed despite changes in drug metabolism, absorption, and distribution with increasing age.
 
Neratinib is a potent oral small molecule that inhibits HER1, HER2 and HER4 at the intracellular tyrosine kinase domains through irreversible binding at a targeted cysteine residue in the ATP binding pocket of the receptor. Both the ability of neratinib to concurrently block signal transduction through the three active tyrosine kinase HER receptors, and its irreversible binding and prolonged inhibition of these growth-promoting pathways, provide the opportunity to further improve the clinical benefit of its use in HER2+ MBC patients. Early clinical data have demonstrated the activity of neratinib in patients who have already progressed through treatment with other small molecule or antibody-based HER2 targeted therapies. With the promising results from multiple clinical trials, neratinib has the potential to emerge as a novel therapy for patients with HER2 positive breast cancer. There is significant interest in studying this drug among older adults, as it is a targeted therapy which is convenient to prescribe and easy to administer. However, there is a significant amount of GI toxicity. In particular, grades 1-4 diarrhea occurred in 92% of patients. Grade 3-4 diarrhea occurred in over 30% of patients and dose reductions secondary to diarrhea range from 20-53% across 9 trials of neratinib alone or in combination with other therapy [1-9]. This particular side effect is likely to be significant in the population of older adults who are particularly vulnerable to diarrhea. Currently, there are 6 trials of neratinib therapy with a total enrollment of 291 patients, but only 38 patients are 65 and older (data provided by PUMA). Therefore, there is a significant gap of knowledge regarding the toxicity profile of neratinib in older adults, as well as the optimal supportive care medications to minimize side effects.

Objectives:
Primary Objective:
To estimate the rate of grade 2 or higher toxicities attributed to neratinib in adults 60 years and older with HER2 overexpressing breast cancer.
Secondary Objectives:

 
• To describe the full toxicity profile including all grades as measured by NCI CTCAE v.4.0.
 
• To estimate the rate of all grades of GI toxicities such as diarrhea, nausea, and vomiting.
 
• To estimate the rate of dose reduction, holds and hospitalizations.
 
• To describe pharmacokinetic parameters of neratinib in adults 60 and older.
 
• To estimate overall response rate (ORR) and clinical benefit rate (CBR) defined by RECIST 1.1.
 
• To estimate event free survival (EFS), progression free survival (PFS) and overall survival (OS).
 
• To evaluate the role of cancer-specific geriatric assessment tool in predicting treatment toxicities.
 
• To estimate adherence rate to neratinib in older adults.
 
• To explore the association of PK parameters and geriatric assessment findings.
 
• To explore if serum biomarkers of aging (IL-6, CRP, and D-dimer) are associated with treatment toxicities.
 

Endpoints:
Primary: Grade 2 or higher toxicities.
Secondary:

 
• All grade toxicities as measured by NCI CTCAE v.4.0.
 
• All grades of GI toxicities such as diarrhea, nausea, and vomiting.
 
• Dose reduction, holds and hospitalizations.
 
• Effect of age on PK parameters: clearance and volume of distribution and exposure-response relationships on efficacy and safety of neratinib.
 
• Response as defined by RECIST.
 
• EFS(where the event is toxicity or progression), PFS, OS.
 
• Geriatric assessment score
 
• Adherence as defined by pill count.
 
• IL-6
 
• CRP
 
• D-dimer
 

Study Design:
The study will be an open label, single arm, phase II toxicity study of single agent neratinib in order to describe the toxicity profile in patients age 60 and older with HER2 positive

breast cancer. We plan to study 40 subjects, stratified by patient age (with at least 5 patients age 75 years or older, and no more than 15 patients 60-70, in order to assure that we study the entire age range of older adults). As diarrhea has been seen with neratinib, we have established additional guidelines and criteria which will be used to flag an unexpected number of patients that experience grade 3 diarrhea within the 2 cycles on neratinib treatment in the presence of aggressive mandatory anti-diarrhea management which will lead to a careful data review. There will also be one interim analysis of the toxicity profile after 20 subjects have been on drug for at least one cycle.

Patients are anticipated to participate in the study for an average of 48 months. This includes approximately 0.5 months for screening, an estimated average of 9.5 months for the active treatment phase, and an estimated average of 38 months for the long-term follow-up phase. Treatment is to be given for as long as it is tolerated and while there is no disease progression. Patients who permanently discontinue treatment will enter the long-term follow-up phase until death or withdrawal of consent.

**Sample Size:**

40

**Estimated Duration of the Study**

48 months

**Summary of Subject Eligibility Criteria:**

Inclusion Criteria:

1. Female or male patient age  $\geq$  60 years.
2. ECOG performance 0-2. (see Appendix A for ECOG criteria)
3. Life expectancy of greater than 12 weeks.
4. Histologically or cytologically proven metastatic breast cancer (metastases can be proven with imaging results in certain circumstances provided that the initial tumor was demonstrated histologically).
5. Stage IV Her2/Neu positive breast cancer patients who failed previous anti-HER2 targeted therapies.
6. HER2 positivity as defined by ASCO/CAP guidelines.

If HER2 negative by IHC or FISH, but activating somatic mutations of HER2 gene identified through genomic sequencing (CLIA certified lab test) including but not limited to the following: Missense substitutions (G309A, G309E, S310F, S310Y, S653C, V659E, R678Q, V697L, T733I, L755S, L755P, D769H, D769Y, D769N, G776V, G776C, V777L, L841V, V842I, R849W, L869R); Insertions/deletions (A775\_G776insYVMA aka Y772\_A755dup, G776VinsC, G776AinsVGC, G778\_S779insCPG, P780\_781insGSP aka G778\_P780dup, L755\_T759del) and/or HER3 activating mutations.

1. There is no limitation on the number of prior lines of systemic therapy or HER2-targeted therapies (prior neratinib not allowed).
2. Both measurable as well as non-measurable disease will be allowed.
3. Adequate organ and bone marrow functions defined below within 4 weeks of pre-

## registration:

- Hemoglobin:  $\geq 9$  g/dL (after transfusion, if necessary).
- Total bilirubin: within normal institutional limits.
- AST (SGOT)/ALT (SGPT):  $\leq 2.5 \times$  institutional upper limit of normal.
- Creatinine clearance  $\geq 30$  mL/min as calculated by Cockcroft-Gault formula.

4. Baseline left ventricular ejection fraction LVEF  $\geq 50\%$  as evaluated by echocardiogram (ECHO) or multiple-gated acquisition scan (MUGA).
5. All grade  $\geq 2$  toxicities other than alopecia from prior therapy have resolved by the time of study commencement.
6. Patient must have completed radiation therapy with adequate recovery of bone marrow and organ functions, before starting neratinib.
7. Patient with stable or treated brain metastases are eligible. Asymptomatic patients with metastatic brain disease who have been on a stable dose of corticosteroids for treatment of brain metastases for at least 14 days are eligible to participate in the study.
8. Provide written, informed consent to participate in the study and follow the study procedures.

Exclusion Criteria:

1. Prior treatment with neratinib.
2. Concurrent usage of other investigational agents, chemotherapy, or hormone therapy. Prior chemotherapy, hormonal therapy, targeted therapy, and investigational agents are allowed but all toxicities grade  $\geq 2$  must have resolved by the time of study commencement (except alopecia).
3. Any major surgery  $\leq 28$  days prior to the initiation of investigational products.
4. Received chemotherapy or biologic therapy  $\leq 3$  weeks prior to the start of neratinib
5. Active uncontrolled cardiac disease, including cardiomyopathy, congestive heart failure (New York Heart Association functional classification of  $\geq 2$ , including individuals who currently use digitalis specifically for congestive heart failure ), unstable angina, myocardial infarction within 12 month of enrollment or ventricular arrhythmia.
6. Concurrent use of digoxin due to cardiac disease. QTc interval  $\geq 450$  milliseconds in men or QTc interval  $\geq 470$  milliseconds in women within 2 weeks of registration or known history of QTc prolongation or Torsades de Pointes.
7. Inability to take oral medication.
8. Other malignancy within the past 3 years with the exception of: a) adequately treated basal cell carcinoma, squamous cell skin cancer, or thyroid cancer; b) cervix or vulva carcinoma in situ; c) cancer considered cured by surgical resection or unlikely to impact survival during the duration of the study, such as localized transitional cell carcinoma of the bladder, or benign tumors of the adrenal or pancreas.
9. Significant chronic gastrointestinal disorder with diarrhea as a major symptom (e.g., Crohn's disease, malabsorption, or Grade  $\geq 2$  National Cancer Institute [NCI] Common Terminology Criteria for Adverse Events Version 4.0 [CTCAE v.4.0] diarrhea of any etiology at baseline).
10. Known clinically active infection with hepatitis B or hepatitis C virus.

11. Evidence of significant medical illness, abnormal laboratory finding or psychiatric illness/social situations that would, in the Investigator's judgment, makes the patient inappropriate for this study.

#### **Investigational Product Dosage and Administration:**

Neratinib will be given as 240 mg (six 40 mg tablets) orally, once daily with food, preferably in the morning, continuously throughout the study period, with no rest between cycles. This medication will be continued until disease progression, death, drug intolerance or other limiting factors, removal from protocol due to patient or physician preference, or loss to follow-up.

#### **Clinical Observations and Tests to be Performed:**

Patients who fulfill the eligibility criteria described above will undergo the full informed consent process. Prior to starting treatment, all subjects will undergo history and physical exam, and laboratories including CBC, chemistry, and liver function tests. Pathology will be reviewed and HER2 receptor status will be documented. HER 2 receptor somatic mutations will be documented if available. Baseline disease will be documented with CT scan of chest, abdomen and pelvis, or PET-CT as long as there is a diagnostic CT component (within 30 days prior to starting treatment). All subjects will have cardiac function evaluation (within 30 days prior to starting treatment) using either an echocardiogram or MUGA scan and an EKG.

Each cycle will be four weeks with neratinib 240 mg orally continued daily. During each cycle, history and physical, CBC and CMP (BMP, LFTs) will be performed once every 4 weeks (+/- 1 wk). Toxicity will be evaluated at these appointments as well between visits if the subject contacts the participating clinician with concerns. Evaluations will continue once per cycle until disease progression, death, discontinuation of the drug, or loss to follow-up.

Due to the risk of diarrhea in this population, research nurse will contact the patient on each day days 1-3 to check on diarrhea and loperamide compliance. During the first cycle (Cycle 1 Day 8 and Day 15) and part of the second cycle (Cycle 2 Day 15, the patient will be seen at a brief nurse visit during those weeks in which no full physician assessment is required. During these visits, adverse events, limited history and physical exams will be done to ensure that any severe side effects that could benefit from intervention are identified.

While on study, CT of the chest, abdomen, and pelvis (or PET-CT as above); and LVEF evaluation will be performed at the end of every three cycles (every 12 weeks). The modality of cardiac evaluation must be consistent throughout the study for each individual patient.

A cancer specific geriatric assessment will be performed at baseline, after 3 cycles, and at the end of the study. The comprehensive cancer-specific geriatric assessment includes an evaluation of functional status, co-morbidity, cognition, psychological status, social functioning and support, and nutritional status.[10] Patients receiving at least 1 dose of investigational product will be evaluable for safety. Safety will be assessed based on medical history, vital sign measurements, physical examination findings, ECG results, MUGA or ECHO and laboratory assessments. Adverse events (AEs) will be graded

according to the NCI CTCAE v.4.0. AEs and SAEs will be reported until 28 days after the last dose of investigational product and will be followed until resolution or until condition stabilizes. Should an investigator be made aware of any neratinib-related SAE occurring any time after the reporting period, it should be promptly reported.

Adherence to neratinib will be measured by pill count at each appointment as well as by patient self-report in dedicated patient diaries, also to be evaluated at each interim visit. Neratinib log will also be utilized to track the use of the pill. In the event of discrepancy in these measures of adherence, we will follow whichever indicates the lower measure of adherence (i.e. if patient states they took 13 of 14 doses, but only 10 doses are missing, we will count the patient as having taken only 10 days. Alternatively, if 14 doses are missing, but the patient stated she only took 11 doses, we will count the patient as having taken only 11 doses.) Measures of patient initiated dose reduction will be exclusively measured by patient self-report. All toxicity related dose interruptions or reductions, hospitalizations, and adverse events will be noted. Subjects will be followed for toxicity outcomes for an additional 30 days after stopping the drug and until resolution of all grade  $\geq 2$  toxicities.

Pharmacokinetic measures will be determined in all study participants. Based on a neratinib half-life of 11-20 hours at steady state, PK samples will be collected at the following time points: Cycle 1 Day 15 pre-dose ( $\pm$  20 minutes), 6 hours post-dose  $\pm$  60 minutes ) and Day 1 of Cycle 3 and 4 pre-dose ( $\pm$  20minutes). All pre-dose samples should be collected within 30 minutes before the daily dose. In the event that the neratinib dose is held or the dose level is changed, pharmacokinetic sample will be rescheduled accordingly.

Mandatory Peripheral blood biomarkers (IL-6, CRP, and D-dimer) and proteomics analysis will be performed at baseline, after 3 cycles, and at the end of the study.

#### **Statistical Considerations:**

Tables will be created to summarize the toxicities and side effects by organ system, attribution and severity for all participants that receive at least one dose of neratinib. Rates and associated 95% exact Clopper and Pearson binomial confidence limits will be estimated for 1) grade 2 or higher toxicities attributed to neratinib, 2) all grade GI toxicities (diarrhea, nausea and vomiting), 3) dose reductions, holds and hospitalizations, and 4) the objective response (CR+PR) and clinical benefit (CR+PR+SD) and 5) 16 week progression free survival(PFS). EFS, PFS and OS will be estimated using the product limit method of Kaplan and Meier. Descriptive statistics will be provided for pharmacokinetic parameters, drug adherence and participant demographics. Generalized linear models and graphical methods will be used to explore factors as identified by a cancer-specific geriatric assessment and serum biomarkers that may be predictive of toxicity dose reductions, dose holds or hospitalizations. We will use generalized linear models to determine if any of these factors independently predict toxicity, response, and/or pharmacokinetic parameters of interest.

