**Table 14. PK Sample Collection Time Points**

PK sample collection	Cycle 1 Day 15 ( $\pm$ 1day)	Cycle 3 Day 1 ( $\pm$ 3days)	Cycle 4 Day 1 ( $\pm$ 3days)
Collection time	Pre-dose ( $\pm$ 20 minutes); 6 hours post-dose ( $\pm$ 60 minutes)	pre-dose ( $\pm$ 20 minutes).	Pre-dose ( $\pm$ 20 minutes).

At each of the required time points, 10 mL venous blood will be collected into a tube containing K2EDTA. Samples will be inverted several times and kept on ice until processing can begin. Plasma will be separated from whole blood by centrifugation at 1,500 x g for 10 minutes at 4° C and ten approximately equal aliquots (300 uL minimum) will be transferred to appropriately-labeled polypropylene tubes and maintained on wet ice until frozen at  $\leq$  -70°C until shipping. Specimens will be batched at each participating site and stored in freezers at each site. At City of Hope, the specimens will be stored in a freezer accessible only to members of the City of Hope pharmacokinetic staff working under the auspices of [name]. Each tube will be labeled with the study number, patient registration number, time point, and the date and time the sample was drawn.

At end of study, a shipment of frozen serum samples at each site will be packed in the shipping container in sufficient dry ice to last at least 3 days (typically 6-8 kg). The container will be sealed and shipped along with the packing worksheet via courier to:

Covance Bioanalytical  
 [name]  
 Madison, Wisconsin 53704-2523;  
 [contact]

Concentrations of neratinib will be measured in plasma with a validated assay method.

NONMEM, a statistical software program that uses non-linear, mixed effects models to determine PK parameters (clearance and volume of distribution), the inter- and intra-patient variability and the population variability in the parameter estimates will be used for this analysis. Random sources of error, intrinsic factors (e.g., age, sex, race, body weight, liver function and renal function) and extrinsic factors (e.g., concomitant medications such as proton pump inhibitors, digoxin, or anti-infectives) will be evaluated to identify factors that contribute to the observed variability in the PK parameter estimates.

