A population pharmacokinetic-pharmacodynamic analysis of neratinib efficacy and tolerability endpoints will be performed in this patient population. The final PK data will be used to generate post-hoc neratinib patient-level plasma PK profiles, from which patient-level neratinib area under the curve (AUC) and maximum plasma concentration (Cmax) exposure metrics will be estimated. Neratinib dose and estimated AUC and Cmax exposure metrics will then be used to complete an exploratory data analysis of potential exposure-response relationships for efficacy and safety endpoints.

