### **15.1 Sample Size and Accrual Rate**

Given a sample size of 40 subjects the widest half-width of the 95% confidence limits for the rate of grade 2 or higher toxicities will be less than or equal to 0.16. For example if we saw a toxicity rate of 0.2 (8 subjects/40) the 95% lower and upper confidence limits would be .09 and .36, respectively. With a sample size of 40, we would expect to see toxicity that has a true rate of occurrence of 0.05 in 87% of trials. We expect an accrual rate of 3 subjects every 2 months, for a total accrual rate of 18 subjects per year. With this rate, the full complement of 40 subjects will be accrued over a 30 month period. The median number of cycles for this patient population is approximately 9, so we would expect to complete this study in 42 to 48 months.

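### Geriatric and biomarker effects on clearance and volume should be estimated inside the population PK model, not by regressing post-hoc patient values

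*Combined protocol and SAP*

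**What the plan says.** The Statistical Considerations of the synopsis and Section 15.3 (Data Analysis) carry the same sentence: generalized linear models will determine "if any of these factors independently predict toxicity, response, and/or pharmacokinetic parameters of interest". The factors, from the sentence before it, are those identified by the geriatric assessment and the serum biomarkers. A secondary objective is "To explore the association of PK parameters and geriatric assessment findings", and Section 1.6.2 adds the association of IL-6, CRP and D-dimer with PK.

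What the PK parameters are is given elsewhere. The secondary endpoints (synopsis and Section 3.2) list "Effect of age on PK parameters: clearance and volume of distribution", and Sections 11.1 and 15.3 name the same two parameters.

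Sampling is sparse: a trough and a 6-hour sample on Cycle 1 Day 15 (Table 14), then "Day 1 of Cycle 3 and 4 pre-dose". Section 11.1 obtains CL and V from a NONMEM mixed-effects model and evaluates there "intrinsic factors (e.g., age, sex, race, body weight, liver function and renal function", together with co-medication. Geriatric scores and the three biomarkers are not named in that list. On individual values, Section 11.1 says: "The final PK data will be used to generate post-hoc neratinib patient-level plasma PK profiles". From these profiles AUC and Cmax are derived for exposure-response work. No shrinkage check is stated.

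**The concern.** Three troughs and one 6-hour sample do not allow CL and V to be calculated directly for each patient. If they are to be outcomes in a generalized linear model, the values would in practice be the post-hoc (empirical Bayes) estimates. These are pulled toward the population mean, more so for the parameter the samples inform less, and their errors in CL and V are correlated.

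A second-stage regression on such values can do two things: understate a true effect, and move part of it onto the other parameter with the sign reversed. The geriatric factors are central to this trial, yet the text sends them to the weaker method, while age and organ function are evaluated in the NONMEM analysis. At stake is whether the exploratory PK-geriatric results give the right size and name the right parameter.

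**Working it through.** The documents give no shrinkage, precision or power figure for these regressions, so there is no planned figure to reproduce. The size was assessed by simulation.

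**Inputs from the documents.** 40 patients (Section 15.1); four steady-state samples at trough, 6 h, trough, trough (Table 14); once-daily dosing; half-life 14 h and absorption within 4 to 6 h (Section 1.4.5.2), represented by an absorption rate of 0.5/h, which puts the peak at about 5 h.

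**Assumptions not in the documents.** One-compartment oral model; population parameters known; between-patient SD of log CL and log V both 0.3 or both 0.5; SD of log absorption rate 0.5; residual SD 0.2 to 0.5 on the log scale; one standardised factor whose true effect is 0 or half a between-patient SD; in one setting 40% of patients lack both later troughs. 1000 trials per scenario, two-sided 5% tests.

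**Formulas.** Shrinkage = 1 - SD(post-hoc)/SD(true). In the linear approximation with uncorrelated CL and V:
- share of a true slope kept = (1 - shrinkage)²
- slope leaked from CL to V = r × (1 - shrinkage of CL) × (1 - shrinkage of V) × (SD of V / SD of CL) × true CL slope, where r is the correlation of the post-hoc values.

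**Results of regressing post-hoc values.** Columns 2 and 3: the factor affects CL only. Columns 4 and 5: it affects V only. Column 6: it affects neither.

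| Between-patient SD / residual SD | CL slope kept | False V | V slope kept | False CL | Rejection for CL / V, no effect |
|---|---|---|---|---|---|
| 0.3 / 0.2 | 0.132/0.15 = 88% | 9.3% | 0.063/0.15 = 42% | 6.9% | 4.5% / 5.8% |
| 0.3 / 0.4 | 0.119/0.15 = 79% | 25.2% | 0.035/0.15 = 23% | 11.7% | 5.7% / 6.0% |
| 0.5 / 0.3 | 0.226/0.25 = 90% | 8.2% | 0.115/0.25 = 46% | 7.0% | 5.3% / 5.6% |
| 0.5 / 0.5 | 0.207/0.25 = 83% | 15.5% | 0.080/0.25 = 32% | 8.7% | 4.7% / 4.4% |
| 0.3 / 0.4, 40% without later troughs | 0.109/0.15 = 73% | 21.5% | 0.034/0.15 = 23% | 10.3% | 4.9% / 5.7% |

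Shrinkage was 5-17% for CL and 33-57% for V. The Monte Carlo standard error at 5% is √(0.05 × 0.95/1000) = 0.7 points, so the last column shows no inflation.

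**Check against the formulas.** In the 0.3 / 0.4 setting with an effect on V only, V shrinkage is 0.51: (1 - 0.51)² = 0.24, against 0.23 simulated. With an effect on CL only, r = -0.51, shrinkage is 0.12 (CL) and 0.56 (V), and the total SD of CL is √(0.3² + 0.15²) = 0.335: -0.51 × 0.88 × 0.44 × (0.3/0.335) × 0.15 = -0.027, as simulated. A true positive effect on CL thus appears as a negative one on V.

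**Second simulation.** With between-patient and residual variability both 30-50% and population parameters known, 23-49% of a V slope and 76-94% of a CL slope were kept. False V associations occurred in 6-48% of trials, false CL associations in 7-16%, and rejection of an unrelated factor in about 3-6%.

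**Factor estimated inside the mixed model (first simulation).** The median slope was 97-102% of truth for CL and 81-96% for V. Rejection on the unaffected parameter was 3.5-5.7%, and with no effect at all 2.8-5.9%. It is not perfect: with an effect on CL only, the median V slope was 0.011 to 0.044 where the truth is 0. Power was 57-81% for CL and 17-41% for V, against 70-79% and 25-50% with post-hoc values.

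**The case against.** - **The text does not name the outcome.** Section 11.1 uses the post-hoc profiles for AUC and Cmax, as predictors in exposure-response work. A reader might infer that it prescribes post-hoc CL and V as regression outcomes; it does not. This stands as a limit on the claim. The inference is still sound, because the plan describes no other patient-level source. If the outcome were CL alone, or AUC, which at a given dose is determined by apparent clearance, only the mild attenuation would apply.
- **False associations.** A reader might infer that the two-step method produces spurious findings in general. It does not: an unrelated factor is rejected at about 5%. The excess is leakage, and needs a true effect on the other parameter.
- **Power.** A reader might expect the in-model test to find more. These results do not support that. When a factor affects both parameters, the comparison depends on how the between-patient covariance is specified. With the induced variance and correlation included, power for V was 49-81% post-hoc against 47-78% in-model; leaving them out lowered the post-hoc figure to 6-26%. Low power for V comes from the sparse design.
- **Already handled in part.** The factor list in Section 11.1 is open-ended and does not exclude geriatric or biomarker factors. That is true, but Section 15.3 and the synopsis explicitly assign them to generalized linear models.
- **Pooling.** Section 15.3 places the samples in a larger population dataset. This improves the population parameters but does not remove individual shrinkage; both simulations already took those parameters as known.
- **Low stakes.** The aim is exploratory, and no dose, stopping or primary-endpoint decision is tied to it. This stands, and it sets the weight of the point.

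**Conclusion.** The point holds as a cheap improvement to an exploratory secondary analysis. If the planned regressions use post-hoc values, as the sampling all but requires, effects on V would be reported at about a quarter to a half of their size and effects on CL at about three quarters to nine tenths. A real effect on one parameter can also surface on the other with the opposite sign: roughly 6-48% false V associations when only CL is affected and 7-16% false CL associations when only V is affected, against a nominal 5%. The case rests on bias and misattribution.

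Every percentage depends on the assumed variances, on the one-compartment model and on known population parameters; the documents give none of the variances. It would be wrong to extend the point to the planned age effect or to organ function, which Section 11.1 already evaluates in the NONMEM analysis, or to the primary toxicity endpoint.

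**What to change.** In Section 15.3 and the synopsis, state that the effects of the baseline geriatric score and baseline IL-6, CRP and D-dimer on apparent clearance and volume (CL/F and V/F) will be estimated as covariates inside the population PK model of Section 11.1, with confidence intervals. Report shrinkage for CL and V. Use post-hoc values for graphics and description only, not for slopes or tests. The generalized linear models for toxicity and response are unaffected.

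The cost is a wording change and a few extra NONMEM covariate runs, with no new samples or patients. Effects on V will remain imprecise because sampling is sparse, and the report should say so.
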